2.5 Sample Size

A total of 250 participants will be randomized: 100 for each of the GMRx2 doses and 50 for placebo group. As noted in Section 12.3 of the protocol, for the comparison of triple $\frac{1}{2}$ vs placebo at week 4, a sample size of 150 participants at a ratio of 2:1 will provide 99.7% power to detect a difference of at least 9 mmHg in mean home SBP, assuming a standard deviation of 11 mmHg. Similarly for the comparison of triple $\frac{1}{2}$ vs placebo at week 4, a sample size of 150 participants at a ratio of 2:1 will provide 100.0% power to detect a difference of at least 13 mmHg in mean home SBP, assuming a standard deviation of 11 mmHg. Therefore, the power for the two comparisons versus placebo will be 99.7% (since $0.997 \times 1.0 = 0.997$). Note that this is a simple, conservative sample size calculation by intention – the actual experimental design and subsequent statistical modelling approach will provide greater power than this.

2.6 Changes in the Conduct of the Study or Planned Analyses

2.6.1 Changes in the Conduct of the Study

A total sample size of 250 participants was planned; however due to a number of high recruiting centres starting at a similar time towards the end of the study a total of 295 participants were randomized.

2.6.2 Changes in Planned Analysis

Multiple analysis sections have been expanded within this document from the protocol-specified analyses. Clarifications and expansions include:

- The addition of an Estimands Section
- Detailed descriptions of mixed models for repeated measures and multiple imputations
- Clarified calculation methods for derivation of primary endpoint
- Use of multiple populations for analysis, including the use of supportive and sensitivity analysis
- Expansion of analysis methods to be used for secondary efficacy and secondary safety endpoints

3 STATISTICAL ANALYSIS

3.1 Interim Analyses

No formal, unblinded interim analysis was planned. Observed standard deviation of the home BP measurements on the overall sample were computed to support updated power calculations periodically

through the study. No modifications to the study were made.

3.2 Multi-Center Trials

Analysis of demographic and baseline characteristics, efficacy and safety data will be pooled across all sites.

For the primary analysis, mixed models for repeated measures (MMRM) will be applied accounting for correlation between observations within site.

3.3 Multiplicity Adjustment

All tests are to be two-sided with a nominal level of α set at 5%. Since the purpose of the trial is to demonstrate effects on both of the GMRx2 dose versions versus placebo comparisons simultaneously for the designated primary endpoint (i.e., each GMRx2 dose has to be statistically significantly superior at two-sided $p<0.05$ to placebo for the trial to be regarded as positive), there is no need for adjustment of the Type I error for the primary endpoint, according to ICH E9 Guidance and FDA Guidance 'Multiple Endpoints in Clinical Trials. Guidance for Industry, 2022'.

The secondary efficacy parameters measure different aspects of the same underlying treatment effect evaluated in the primary efficacy endpoint, that is the effect of GMRx2 compared to placebo on blood pressure and do not demonstrate additional new treatment effects of the drug, but rather clarify the effect already demonstrated by the primary analysis. No type I error adjustment is proposed to adjust secondary efficacy endpoint analyses.

3.4 Populations for Analysis

3.4.1 Screened Set

The Screened Set includes all participants who have provided consent and have a screening number, regardless of whether they have been randomized or treated with study treatment.

3.4.2 Safety Set

The Safety Set is defined as all participants who took at least one dose of study treatment, including during Period 1 single-blind run-in. For the analysis of the safety endpoints, participants will be analyzed in the treatment group they actually received.

3.4.3 Efficacy Populations

For all efficacy analyses participants will be analyzed in the treatment group to which they have been randomized.

The Randomized Set will be the set of reference for reporting primary and secondary endpoints to preserve the intention-to-treat (ITT) principle. The Full Analysis Set (FAS) and other strategies proposed will be used to evaluate the robustness of the results and primary conclusions of the trial.

3.4.3.1 Randomized Set

The Randomized Set includes all participants who have been randomized. Participants will be analyzed in the treatment group to which they have been randomized.

3.4.3.2 Full Analysis Set

The FAS is defined as all participants in the randomized set who have taken at least one dose of randomly assigned treatment. Participants will be grouped according to the treatment assigned. If the Randomized Set and the FAS are very similar in size ($\leq 5\%$ difference), the efficacy analysis will not be rerun on the FAS set as a sensitivity analysis.

3.4.3.3 Per Protocol Set

The Per Protocol Set is defined as all randomized participants who did not experience an intercurrent event or major protocol deviation. Intercurrent events are defined within the Estimand Statements ([Section 3.10.1](#)). Major protocol deviations are defined in [Section 3.9.3](#).

3.5 General Methods

All data listings that contain an evaluation date will contain a relative study day. Two relative study days will be defined: Period 1 Relative Day (P1 Rel Day) and Post-Randomization Relative Day (PR Rel Day). For Period 1 Relative Day, pre-treatment (screening) and on-treatment (run-in and post-randomization) study days are numbered relative to the day of the first dose of single-blind placebo which is designated as P1 Day 1. The preceding day is P1 Day -1, the day before that is P1 Day -2, etc. Post-Randomization Relative Day will be numbered relative to the day of the first dose of the randomized medication which is designated as PR Day 1.

The planned treatment group for all participants in Period 1 is placebo. In Period 2, the planned treatment group is randomly assigned to be:

1. **Triple $\frac{1}{4}$ (GMRx2):** telmisartan 10 mg/amlodipine 1.25 mg/indapamide 0.625 mg
2. **Triple $\frac{1}{2}$ (GMRx2):** telmisartan 20 mg/amlodipine 2.5 mg/indapamide 1.25 mg
3. **Placebo**

All output will be incorporated into Microsoft Word or Adobe Acrobat PDF files, sorted and labelled according to the ICH recommendations and formatted to the appropriate page size(s).

Tables will be produced for appropriate demographic, baseline, efficacy and safety parameters. For categorical variables, summary tables of the number and percentage of participants within each category (with a category for missing data) of the parameter will be presented. For continuous variables, the number of participants, mean, median, standard deviation (SD), minimum and maximum values will be presented. Summarizations will be presented by treatment group and overall. For safety summaries, Period 1 (placebo run-in period) will be summarized separately from the randomized treatment period and follow-up. Efficacy summaries will not be created for Period 1.

3.5.1 Computing Environment

All descriptive statistical analyses will be performed using SAS statistical software using version 9.4 or higher, unless otherwise noted. Medical history and adverse events will be coded using the Medical Dictionary for Regulatory Activities (MedDRA) Version 24.0 (or higher, as up-versioning may occur). Concomitant medications will be coded using the World Health Organization (WHO) Drug Dictionary March 2021 version (or later, as up-versioning may occur).

3.5.2 Baseline Definitions

For Period 1, Baseline for safety and in-clinic assessments is defined as the most recent measurement prior to the first administration of placebo run-in study treatment.

For in-clinic efficacy parameters, including change from baseline measurements at post-Randomization timepoints, Baseline is the last Clinic BP measurement occurring prior to the first dose with randomized

study treatment.

Baseline for home SBP measurements is defined as measures taken during the week prior to Randomization, with derivation defined in [Table 3-2](#).

3.5.3 Study Period for Analysis

The study is planned with 3 periods ([Section 2.2.3](#)) with varying treatment assigned in both trial medication and dose level during the specified periods. For a minority of participants, FU1 may not occur at 4 weeks exactly and screening visit is not always exactly 2 weeks before Randomization visit, due to protocol-specified visit windows and administrative issues such as scheduling issues for participants. Therefore, the analysis periods will be defined:

- Period 1: From Week -2 to Randomization, defined as from screening to Randomization and Baseline Visit,
- Period 2: From Randomization to Week 4, defined as from Randomization and Baseline Visit to FU1/Week 4 visit,
- Period 3: From Week 4 to Week 8, defined as from FU1/Week 4 to EOT/Week 8,
- Post-Randomization Period: From Randomization to Week 8, defined as from Randomization and Baseline Visit to FU2 (Period 2 and Period 3).

Analysis of the optional Open-Label Extension Study will be described in a separate analysis plan.

3.6 Subject Disposition

All participants screened who met study inclusion criteria for placebo run-in (Period 1) will be accounted for. The number of participants who were randomized; and reasons for exclusion for non-randomized participants will be summarized.

Subject disposition will be tabulated for the following categories and will include all participants in the Screened Set:

- Number (%) of participants screened
- Number (%) of participants entered run-in period
- Number (%) of participants randomized
- Number (%) of participants randomized, ineligible for randomization
- Number (%) of participants randomized but did not receive study treatment
- Number (%) of participants completing Period 2 (defined as attending Week 4, Visit FU1)
- Number (%) of participants completing the trial, including safety follow-up
- Number (%) of participants prematurely and permanently discontinuing the study treatment and reasons
- Number (%) of participants prematurely and permanently discontinuing from the trial and reasons
- Number (%) of participants in each analysis population ([Section 3.4](#)).

3.7 Baseline Characteristics

Description of the baseline characteristics will be presented by treatment group and overall. Baseline characteristics will be summarized on the Safety Set by treatment group, Safety Set by Randomization Eligibility and Randomized Set by treatment groups, including the below parameters:

- Demographic characteristics: age (years), sex, race, ethnicity, height (cm), weight (kg), BMI (kg/m²), country/region, education
- Lifestyle: Smoking status and alcohol consumption
- 12-lead ECG: Interpretations will be tabulated
- Screening visit: Number of prior BP medications

The following parameters will be summarized:

- Demographic characteristics, lifestyle and 12-lead ECG
- Screening visit: Clinic BP (SBP and DBP)
- Change from Screening Visit to Randomization in Clinic BP (SBP and DBP)
- Average home BP at Randomization (end of Period 1 SBP; See [Table 3-2](#) for derivations)
- Change in average home BP from first to last week of Period 1

Medical history will be provided in by-participant data listings. Summaries may also be presented.

3.8 Prior/Concomitant Medications

Prior and concomitant medications will be summarized by treatment group. Prior medications are medications that were being taken at the time of screening. Concomitant medications are medications that started or were ongoing from run-in period to the end of trial. Concomitant medications will be summarized separately for medications taken during Period 1 (pre-Randomization) and post-Randomization.

Prior/Concomitant medication will be summarized using descriptive statistics:

- Number (%) of participants with at least one prior medication, by ACT code level 1 and preferred term
- Number (%) of participants with at least one concomitant medication during Period 1, by ACT code level 1 and preferred term
- Number (%) of participants with at least one concomitant medication post-Randomization, by ACT code level 1 and preferred term
- Number (%) of participants with at least one concomitant BP lowering medications post-randomization, by ATC code level 1 and preferred term.

Concomitant medications will be summarized by Anatomical Therapeutic Chemical (ATC) term according to the WHO Drug Dictionary (WHO DD) (March 2021 version or later if up-versioning occurs) used for drug coding (https://www.whocc.no/atc_ddd_index/).

3.9 Adherence

3.9.1 Adherence to Trial Medication

The planned daily dose is 1 pill per day. Adherence to trial medication will be computed overall and separately for each randomized group.

Trial medication adherence will be computed separately for the 2-week run-in period and the post-randomization treatment period (from randomization to FU1/Week 4) and will be assessed using the following parameters:

- Denominator: Planned number of pills for the period is defined as the number of days between the scheduled first and last treatment intake. The medication log CRF will be used to determine the number of expected days by computing the number of days between the start and stop dates for each record and summing across all records reported for each participant. Note, if there is a gap between the stop and start records for sequential medication logs, gap days will be assigned an expected count of 0.
- Numerator: The number of pills taken is measured via pill counts and numbers of pills returned. For participants with missing pill-return data, it will be assumed that the number of pills taken equals the minimum of the number of pills dispensed for that period and the number of days between the logged start and stop dates for the corresponding trial medication log.

Adherence to trial medication will be calculated as numerator/denominator and expressed in percentage. Adherence is confirmed if $\geq 80\%$ and $\leq 120\%$.

Additional details surrounding the calculations of numbers of pills dispensed and adherence will be described in a separate specifications document.

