8.4.3. Optional Open-Label Extension Period

In a subset of sites, participants who are still receiving study medication at Week 4 will be invited to continue on to an optional Open-Label Extension Period with the aim to assess effectiveness, safety and adherence over a 52-week period. Willing participants will enter the Open-Label Extension Period at the Week 4 visit, at which time they will be allocated open-label GMRx2-Dose version 1. Follow-up visits will be conducted at Week 6, 8, 16, 28, 40, and end of Open-Label Extension Period visit at week 52 (See Table 6). Participants will continue to monitor BP at home, once per week until the Week 8 visit, and thereafter on a set day every month (e.g. 1st day of the month) until the week 52 visit. Home BP measurements will be made using a validated, electronic, automatic, digital upper-arm cuff and recorded in a home BP diary, as specified in the Blood Pressure Monitoring Manual of Procedures. During follow-up visits, if home BP from the most recent measurement is above 130 mm Hg for SBP and/or above 80 mmHg for DBP, BP-lowering therapy will be up-titrated in the following order: GMRx2-Dose1 → GMRx2-Dose2 → GMRx2-Dose3 (telmisartan 40mg/amlodipine 5mg/indapamide 2.5mg) → GMRx2-Dose3 plus telmisartan 40 mg/amlodipine 5 mg → GMRx2-Dose3 plus telmisartan 40 mg/amlodipine 5 mg plus spironolactone 25 mg. The rationale for this regimen is based on the evidence indicating that:

- About 80% of the maximum BP-lowering effects of BP-lowering regimens are achieved by 2 weeks⁵⁰
- US hypertension guidelines recommend a home BP target of <130/80 mmHg²⁵
- Up-titration steps should provide clinically meaningful BP reductions – the BP reductions of only 2-3/1-2 mmHg achieved by increasing the dose of a single drug are likely to be only modestly effective and such steps can act as barriers to effectively achieving BP goals.⁵⁰ Doubling the dose of telmisartan 40 mg/amlodipine 5 mg achieves an additional 5/4 mmHg reduction,⁵¹ and the use of concomitant ARB therapy reduces the incidence of pedal oedema associated with higher dose amlodipine.^{59,61} The Pathway-2 trial demonstrated that a mineralocorticoid receptor antagonist is superior to a beta-blocker or an alpha-blocker in patients not controlled on maximal doses of three drugs.⁶²

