8.7. Down-Titration or Temporary Cessation of Randomized Trial Medication

If, during the randomized period a participant develops a condition or symptom likely to be related to the trial medication (e.g. due to possible hypotension) that is severe enough to warrant discontinuation of the trial medication, then the Investigator can choose to discontinue the trial medication temporarily. The reason for discontinuation will be recorded. There is no need to unblind trial medication in this situation. Consideration should also be given to restarting trial medication subsequently, if benefits of restarting outweigh the risks as per the medical condition of the participant. If a participant discontinues medication at his/her own initiative, the reason should be investigated. If medically appropriate, consideration should be given to restarting study

medication.

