3.9.3 Protocol Deviations

Over a blind review meeting, before database lock and unblinding, the different protocol deviations will be classified as minor or major and categorized by type (e.g. non-compliance to treatment, prohibited medication etc.) by the clinical teams. The number of major protocol deviations will be summarized by type of deviations. All protocol deviations will be listed.

Major protocol deviation categories include, but are not limited to:

- Randomized even though ineligible (not including minor non-safety related reasons such as miscalculation of run-in adherence)
- Received the wrong treatment
- Non-adherence to study treatment (adherence $< 80\%$ or $> 120\%$), for reasons known to be unrelated to tolerability or efficacy eg. participant moved overseas
- Interruption to study treatment as a result of supply chain issues in which protocol-specified procedures were not followed,
- Insufficient valid home BP measurements for home blood pressure calculation at randomization or follow-up visit 1.

A summary table will present the tabulations by major protocol deviation on the Screened Set. All protocol deviations will be listed.

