3.10 Analysis of the Efficacy Endpoints

3.10.1 Estimand

3.10.1.1 Primary Estimand

The population for the primary estimand includes adults (aged ≥ 18 years) with hypertension. The variable of interest is the difference between home measured SBP after Week 4 of treatment post-randomization and the home measured SBP in the week prior to randomization. The primary analysis will be performed on the Randomized Set including all participants who were randomized to treatment.

Intercurrent events for the primary analysis are listed below:

- Received the wrong treatment (i.e. a treatment other than the randomly assigned treatment)
- Discontinuation from the study treatment for reasons related to the study protocol or study treatment, such as lack of efficacy, tolerability, or adverse event.

For the primary analysis, the Treatment Policy Strategy will be applied where intercurrent events that do not result in missing BP measurements are considered irrelevant and data will be analyzed regardless of the occurrence of the event. The use of a Treatment Policy Strategy most closely aligns to an ITT analysis, where all available and imputed data contribute toward the estimated treatment effects. Participants with intercurrent events and missing data will have imputations performed from those participants with intercurrent events and non-missing data (Section 3.10.2.6). Participants without intercurrent events and missing data will have imputations performed from those participants without intercurrent events and non-missing data.

The primary analysis will be performed using a mixed model for repeated measures (MMRM). Sensitivity analyses adjusted for covariates are planned for the primary endpoint (Section 3.10.2.3). Subgroup analyses will also be performed among the primary analysis set (Section 3.10.2.5).

Supplemental analyses will be performed among the following analysis sets:

- 1) Full Analysis Set, including participants who have taken at least 1 dose of study treatment post-randomization and applying imputation methods in the same manner as the primary analysis methods (analysis to be performed if samples differ by $>5\%$)

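### SAP 3.9.1 drops participant-led gap days from the adherence denominator when a stop and restart is logged as two records, so 14 of 28 days off drug can score 100% (minor)

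*SAP*

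**What the plan says.** SAP 3.9.1 opens with this denominator: "Planned number of pills for the period is defined as the number of days between the scheduled first and last treatment intake". The operating rule that follows is different. Expected days are the logged start-to-stop days summed over a participant's medication log records, and where there is a "gap between the stop and start records for sequential medication logs, gap days will be assigned an expected count of 0". The rule does not depend on how long the gap is, why it arose or who started it.

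The numerator is capsules taken by pill count. If return data are missing, it is the smaller of the capsules dispensed and the logged days. Adherence from 80% to 120% counts as confirmed. Further calculation details are deferred to a separate specification.

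The figure is used again in SAP 3.9.3. Adherence below 80% or above 120% is a major deviation when it occurs "for reasons known to be unrelated to tolerability or efficacy eg. participant moved overseas". Supply problems have their own category: "Interruption to study treatment as a result of supply chain issues in which protocol-specified procedures were not followed". SAP 3.4.3.3 then limits the Per Protocol Set to "all randomized participants who did not experience an intercurrent event or major protocol deviation".

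Protocol 8.7 foresees temporary stops of two kinds. The investigator may hold the drug for a suspected drug-related problem. Separately, "If a participant discontinues medication at his/her own initiative, the reason should be investigated", and restarting is to be considered if medically appropriate.

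**The concern.** The definition and the operating rule agree when a participant has one continuous record. They diverge when a participant-led interruption creates two. The days off drug are then neither taken nor expected, so the percentage does not show them. The same course entered as one record does show them, so a site's logging habit can decide the result.

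Two outputs are exposed. One is adherence by arm. SAP 3.6 tabulates only permanent discontinuation, so adherence is the main planned summary in which a temporary stop would appear. The other is the Per Protocol Set, which can keep someone who was off drug for much of Period 2 for a reason such as travel.

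The gap rule is not needed to separate run-in from Period 2, because 3.9.1 computes those periods separately. Within Period 2, Protocol Table 5 schedules dispensing only at randomization. A gap between two Period 2 records would therefore plausibly be an interruption, or a replacement of lost or damaged capsules (Protocol 10.2.14).

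**Working it through.** The plan gives no worked adherence figure to reproduce, so the check compares its two denominators directly.

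**Inputs.** One capsule per day (SAP 3.9.1). Period 2 of 28 days, or 21 to 35 with the visit window (Protocol Table 5). Limit 80% (SAP 3.9.3). 295 randomized (SAP 2.6.1) at 2:2:1, taken as exact: 295 × 2/5 = 118 per active arm and 295/5 = 59 on placebo. Effects of 9 and 13 mmHg and SD 11 mmHg (Protocol 12.3). Assumed: inclusive day counting, two log records, all capsules taken outside the gap.

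**Adherence for a gap of g days in D.** Stated definition: (D − g)/D. Gap rule: (D − g)/(D − g) = 100%. For D = 28:

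| Gap (days) | Stated definition | Gap rule, two records |
|---|---|---|
| 5 | 23/28 = 82.1% | 100% |
| 6 | 22/28 = 78.6% | 100% |
| 10 | 18/28 = 64.3% | 100% |
| 14 | 14/28 = 50.0% | 100% |

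The shortest gap that falls below 80% on the stated definition is 5 days in 21 (16/21 = 76.2%), 6 in 28 (78.6%) and 8 in 35 (27/35 = 77.1%).

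**Further missed capsules.** A 14-day gap plus two missed capsules scores 12/14 = 85.7%, which counts as confirmed, instead of 12/28 = 42.9%.

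**Same stop, one record.** A record from day 1 to day 28 with 14 capsules taken gives 14/28 = 50%.

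**Effect on the adherence summary.** Each such participant raises the percentage with confirmed adherence by 100/118 = 0.85 points in an active arm or 100/59 = 1.69 points on placebo. A 14-day gap raises mean adherence by 50/118 = 0.42 or 50/59 = 0.85 points.

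**Effect on the Per Protocol estimate.** Dilution per retained active-arm participant is (1 − f) × effect/n, where f is the share of the effect present at Week 4.
- Off drug at Week 4 (f = 0): 9/118 = 0.08 mmHg for dose 1 and 13/118 = 0.11 mmHg for dose 2. If the Per Protocol arm is 100 (assumed): 0.09 and 0.13 mmHg.
- Back on drug for about two weeks (f = 0.8): 0.2 × 9/118 = 0.015 and 0.2 × 13/118 = 0.022 mmHg. The 0.8 comes from Protocol 8.4.3: "About 80% of the maximum BP-lowering effects of BP-lowering regimens are achieved by 2 weeks".

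The standard error of a dose-placebo difference is 11 × √(1/118 + 1/59) = 1.75 mmHg.

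**The case against.** The strongest reply is that a count of 0 is sometimes right. The definition refers to scheduled intake, and during an investigator-directed hold no capsule is scheduled. For those gaps the rule is a coherent measure of compliance. This stands, and it narrows the point to participant-led gaps.

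The two-record premise is also unproven. No document says how sites log a temporary stop, replacement supply can also create sequential records, and the separate specification is not available. This stands as a limit. It does not remove the rule, because the SAP itself states the zero count without restriction.

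Four stronger readings are tempting, and the documents do not support them.
- A reader might infer that the 80% limit cannot detect interruptions. It does detect one logged as a single record. SAP 3.9.3 also has an open list of categories and a blind review before unblinding, so a gap can be caught another way. In addition, gaps for tolerability or efficacy do not meet the 3.9.3 adherence criterion under either denominator.
- A reader might infer a score of 100% for a gap of any length. That needs inclusive counting. If days are stop minus start, n capsules over two records score n/(n − 2). That is 14/12 = 116.7% for a 14-day gap and 8/6 = 133.3% for a 20-day gap, and the second breaches the 120% limit.
- A reader might think it open whether a temporary stop is an intercurrent event, since SAP 3.10.1.1 lists "Discontinuation from the study treatment for reasons related to the study protocol or study treatment, such as lack of efficacy, tolerability, or adverse event". Protocol 8.8 ties discontinuation of trial medication to permanent cessation, and SAP 2.3.3 lists temporary cessation separately. The distinction largely exists already.
- A reader might fear for the primary result. The primary analysis uses the Randomized Set under treatment policy. Adherence enters only when Week 4 home BP is wholly missing, and SAP Table 3-2 needs just one valid reading in the 7 days.

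**Conclusion.** The concern holds in a narrow form, and its severity is minor. For a participant-led stop and restart logged as two records, the gap rule departs from the SAP's own definition of planned pills. With inclusive counting and the other capsules taken, 14 of 28 days off scores 100% instead of 50%. A gap of 6 or more days in 28, for a reason known to be unrelated to tolerability or efficacy, is then not caught by the 80% criterion.

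This can overstate adherence by arm and keep such participants in a supplemental analysis set. The documents give no interruption rate, so only per-participant sizes can be stated. All are small, and the primary conclusion is not affected. The unknowns are how sites log stops and what the separate adherence specification says.

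**What to change.** In SAP 3.9.1, for Period 2:
- Use as denominator the planned days from first randomized dose to the Week 4 visit. If treatment was stopped permanently for reasons unrelated to tolerability or efficacy, use the scheduled Week 4 date. Otherwise the SAP's own example of a participant who moves overseas could still score 100% on the days before leaving.
- Count participant-led gap days as expected.
- Keep an expected count of 0 only for documented investigator-directed holds and documented supply or administrative gaps.
- Use this one definition for the adherence summary and for the 3.9.3 criterion, and carry no second, conflicting adherence figure.

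No change to the intercurrent-event definition is needed.

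The cost is a few sentences before unblinding, using log dates, pill counts and recorded stop reasons. No new data and no change to the primary model are required. Reported adherence may fall slightly and a few participants may leave the Per Protocol Set. With a single definition, a participant with a long self-initiated gap and no Week 4 home BP at all would also count as non-adherent under rule 3 of SAP 3.10.2.6 and be imputed from placebo. For someone already back on drug, own-arm imputation may fit better, but the case should be rare and its ceiling is 0.08 or 0.11 mmHg per participant, by the same arithmetic as above.
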